## 6. STUDY PROCEDURES

### 6.1 Study Schedule

All required study procedures are outlined in [Appendices A, B, and C](#).

### **6.1.1 Screening**

Written informed consent for the study will be obtained prior to the performance of any study-related procedures including screening procedures. A 4-week period is provided for completing screening assessments and determining patient eligibility for the study. Abnormal screening results may be re-tested once for determination of patient eligibility after consultation with the Sponsor Medical Monitor. Patients may be re-screened 1 time in order to determine eligibility.

During the screening period, patients will undergo a medical history and physical examination including vital signs, 12-lead electrocardiogram (ECG) and have blood and urine samples taken for clinical laboratory testing. Patients will be screened for HIV, hepatitis B, and hepatitis C.

On confirmation of eligibility and prior to randomization, patients will also undergo a 24 hr urine collection for creatinine, albumin, and protein as a baseline assessment.

### **6.1.2 Treatment Period**

Treatment period is defined as the time between the first and the last doses of study drug plus one dosing interval. During the treatment period, patients will report to the study center for clinic visits. Patients will receive 20 mg doses of Study Drug administered by SC injection once every 4 weeks for up to 49 weeks in Cohort A, 40 mg doses of Study Drug administered by SC injection once every 4 weeks for up to 49 weeks in Cohort B, 60 mg doses of Study Drug administered by SC injection once every 4 weeks for up to 49 weeks in Cohort C, 20 mg doses of Study Drug administered by SC injection once every 2 weeks for up to 51 weeks in Cohort D, or 20 mg doses of Study Drug administered by SC injection once per week (weekly) for up to 52 weeks in Cohort E ([Section 8.1](#)).

Collection and measurement of vital signs, physical examination results, ECGs, clinical laboratory parameters ([Appendix B](#)), ISIS 681257 plasma concentrations, immunogenicity and biomarker samples, AEs and concomitant medication/procedure information will be performed according to the Schedule of Procedures in [Appendix A](#).

#### Extensive Pharmacokinetic (PK) Subgroup Only:

Within each cohort, a subgroup of approximately 12 patients, who will consent to extensive PK sampling, will undergo additional PK sampling, in what is referred to as the PK Subgroup in this study. Patients in this subgroup will have additional PK sampling time points in order to evaluate the plasma PK parameters of ISIS 681257. Patients in this subgroup will have additional visits to the clinic during the treatment period in order to collect blood samples for PK assessment ([Appendix C](#)).

### **6.1.3 Post-Treatment Period**

Each patient will be followed for safety assessments for 16 weeks after the treatment period. During the post-treatment follow-up period, patients will return to the Study Center for 3 outpatient visits at Weeks 4, 10, and 16 after the treatment period for safety and clinical laboratory evaluations and for blood sampling for PK ([Appendices A and C](#)).

## 6.2 Additional Study Assessments

### 6.2.1 Laboratory Assessments

Laboratory analyte samples will be collected throughout the study as per the Schedule of Procedures in [Appendix A](#). A list of these analytes is contained in [Appendix B](#).

Routine blood chemistry and urine samples (excluding 24-hour urine collection) should be taken after fasting for at least 10 hours. Any confirmatory test, or test taken for safety reasons, may be taken at any time, irrespective of fasting status. During preparation for fasting samples, the patient can drink water and they should ensure that they consume sufficient water in order to not become dehydrated.

If tests are uninterpretable (e.g., due to clumping, hemolysis or quantity not sufficient) or missing, a repeat blood or urine specimen should be re-drawn as soon as possible (ideally within 1 week).

While on treatment hematology samples will be collected every 14 days. Each time a hematology lab is drawn and sent to the central laboratory for analysis, an additional sample should be collected in parallel and analyzed locally. In the event that both the central and local samples are unreportable (e.g., due to hemolyzed or clumped blood samples), patient dosing cannot continue until another sample is repeated and determined not to have met a platelet stopping rule.

If there is no reportable platelet count within 14 days of the last platelet count, the Investigator will contact the patient to hold dosing until a new platelet count is obtained and reviewed.

While on treatment blood and urine samples for renal function testing will also be collected every 14 days and sent to the central laboratory for analysis, per [Section 8.5.2](#). If there are no test results available within 14 days of the last set of results for parameters considered critical to patient safety, the Investigator will contact the patient to hold dosing until a new test set is obtained and reviewed.

While on treatment liver function testing will also be collected every 14 days and sent to the central laboratory for analysis for the first 3 months of the study treatment, and monthly thereafter during the Treatment Period per [Section 8.5.1](#).

All lab samples sent to the central laboratory are received on the next day and processed. Lab Alerts issued as per protocol safety monitoring requirements or stopping rules will indicate the applicable protocol section to facilitate review and will be immediately and simultaneously sent by email to the Investigator, the Sponsor and the CRO Medical Monitors, the Sponsor Drug Safety Physician, and the Clinical Trial Manager (CTM), and should be received by them within 2 days from sample collection. Hematology results from the site's local laboratories are received by the study center staff on the day of sample collection, and should be entered as soon as possible into the eCRF to inform the Sponsor and CRO study monitoring teams.

All platelet count results must be reviewed promptly (within 24 hours of receipt) by the Investigator, or designee, to ensure that the count has not met the stopping rule and to determine whether the rate of decline is suggestive that the patient could be approaching the dose interruption rule of 75,000/mm^3 as specified in [Section 8.6.3](#). Any case of a platelet count reduction to levels below 50,000/mm^3 (Grade 3 or

Grade 4) is considered an adverse event of special interest and must be reported in an expedited fashion to the Sponsor as per [Sections 9.3.3.1](#) and [9.4.1](#).

All liver and renal function tests must also be reviewed promptly (within 24 hours of receipt) by the Investigator, or designee, to ensure that the result has not met the stopping rule. Any event meeting renal stopping rules criteria described in [Section 8.6.2](#) is considered an adverse event of special interest and must be reported in an expedited fashion to the Sponsor as per [Sections 9.3.3.1](#) and [9.4.1](#).

All lab alerts received, including those related to platelet, liver, or renal function monitoring/stopping rules, are also reviewed promptly by the Sponsor and the CRO Medical Monitors who will agree on actions to be taken. Within 24 hours of receiving an actionable lab alert the CRO Medical Monitor will communicate instructions to the Investigator and the study personnel by emailing them the Safety Surveillance Form that needs to be signed by the Investigator/study personnel and promptly returned to the Sponsor and CRO Medical Monitor. In urgent cases, such as platelets results below 50,000/mm^3, or liver or renal test results reaching a critical stopping rule the Investigator must also be contacted by phone.

Further information on safety monitoring and actions to be taken by the Study Investigator in the event of reduced platelet count are provided in [Sections 8.5.3](#) and [8.6.3](#).

#### **6.2.2 Physical Exams and Vital Signs**

Physical exams and vital signs will be performed as indicated in the Schedule of Procedures ([Appendix A](#)) Vital signs should include weight, blood pressure (BP), pulse rate, respiratory rate and body temperature. BP and pulse rate will be recorded after the patient has been in a sitting position for at least 5 minutes. BP should always be measured on the same arm (preferentially on the left arm). Height will be measured at Screening.

#### **6.2.3 Electrocardiography**

Electrocardiography (ECG) will be conducted at Screening, Day 1, (prior to the first dose of Study Drug), and again during the treatment period as follows per dosing cohort:

- Cohorts A, B, and C at Weeks 5, 13, 21, 25, 33, 41, 49, and 53
- Cohorts D and E at Weeks 5, 13, 21, 27, 33, 41, 49, and 53

In all cohorts, ECGs will be conducted during the post-treatment follow-up period at 4, 10, and 16 weeks after the treatment period.

ECGs will be recorded after the patient has been resting in a supine position for at least 5 minutes. ECGs will be performed in triplicate.

#### **6.2.4 PK Sampling**

Blood samples for the determination of plasma ISIS 681257 concentrations will be collected prior to dosing on Day 1 and at various times throughout the treatment and post-treatment follow-up periods as noted in the tables in [Appendix C](#).

Within each cohort, patients assigned to the PK Subgroup will have additional PK sampling time points and additional visits to the clinic during the treatment period in order to collect blood samples for PK assessment ([Appendix C](#)).

### 6.3 Restriction on the Lifestyle of Patients

#### 6.3.1 Contraception Requirements

All male patients and women of childbearing potential must refrain from sperm/egg donation and either be abstinent† or practice effective contraception from the time of signing the informed consent form until at least 16 weeks after their last dose of study treatment.

Male patients engaged in sexual relations with a female of child-bearing potential must also encourage their female partner to use effective contraception from the time of signing the informed consent until 16 weeks after the patient's last dose of study treatment.

For the purposes of this study, women of childbearing potential are defined as any female who has experienced menarche, and who does not meet 1 of the following conditions:

- Postmenopausal: 12 months of spontaneous amenorrhea in females > 55 years of age or, in females ≤ 55 years, 12 months of spontaneous amenorrhea without an alternative medical cause and FSH levels in the postmenopausal range for the laboratory involved
- 6 weeks after surgical bilateral oophorectomy with or without hysterectomy
- Post hysterectomy

For the purposes of the study, effective contraception is defined as follows:

For male patients:

- Effective male contraception includes a vasectomy with negative semen analysis at Follow-up, or the use of condoms together with spermicidal foam/gel/film/ cream/suppository
- Male patients with partners that are pregnant must use condoms as contraception to ensure that the fetus is not exposed to the Study Drug

For female patients and female partners of male patients:

- Using 2 of the following acceptable methods of contraception: surgical sterilization (e.g., bilateral tubal ligation), hormonal contraception, intrauterine contraception/device, or any 2 barrier methods (a combination of male or female condom\* with diaphragm, sponge, or cervical cap) together with spermicidal foam/gel/film/cream/suppository

†**Note:** Abstinance is only acceptable as true abstinence, i.e., when this is in line with the preferred and usual lifestyle of the patient. Periodic abstinence (e.g., calendar, ovulation, symptothermal, post-ovulation methods), declaration of abstinence for the duration of a trial and withdrawal are not acceptable methods of contraception.

**\*Note: A female condom and a male condom should not be used together as friction between the 2 can result in either or both products failing.**

### **6.3.2 Other Requirements**

All patients will be required to fast for at least 10 hours before visits requiring fasted blood sampling.

## **7. STUDY DRUG**

### **7.1 Study Drug Description**

Study Drug (ISIS 681257 or Placebo) characteristics are listed in [Table 1](#).

Study Drug (ISIS 681257 or Placebo) will be provided as 0.8 mL deliverable volume in 2 mL stoppered and sealed glass vials as a sterile solution.

The Study Drug is clear to slightly yellow in color, it is for single use, contains no preservatives and must be stored between 2 to 8 °Celsius and be protected from light.

#### **7.1.1 ISIS 681257**

ISIS 681257 vials contains 100 mg/mL ISIS 681257 in Water for Injection. Additionally, sodium phosphate buffer and sodium chloride are added to control the measure of the acidity or basicity of the solution (pH) and tonicity, respectively. The target pH is 7.4.

#### **7.1.2 Placebo**

Placebo vials contain 0.9% sodium chloride in Water for Injection. 1.6 µg/mL riboflavin is added to ensure color matching of placebo vials to ISIS 681257 vials.

**Table 1 Study Drug Characteristics**

Study Drug	ISIS 681257	Placebo
Strength	100 mg/mL	Not Applicable
Volume/Formulation	0.8 mL solution per 2.0 mL vial	0.8 mL solution per 2.0 mL vial
Route of Administration	SC	SC

SC = subcutaneous

### 7.2 Packaging and Labeling

The Sponsor will provide the Investigator with packaged Study Drug (ISIS 681257 or placebo) labeled in accordance with specific country regulatory requirements.

### 7.3 Study Drug Accountability

The study staff is required to document the receipt, dispensing, and return of Study Drug (ISIS 681257 or placebo) supplies provided by the Sponsor. The patient must return all used and unused Study Drug to the Study Center for accountability. The Study Center must return all used and unused Study Drug to the Sponsor or designee for destruction. All used syringes must be disposed of as per the site's hazardous waste destruction policy.

## 8. TREATMENT OF PATIENTS

### 8.1 Study Drug Administration

ISIS 681257 will be administered to patients by Study Center staff as follows:

- Cohort A: a single SC dose of 20 mg once every 4 weeks for up to 49 weeks and a maximum of 13 doses
- Cohort B: a single SC dose of 40 mg once every 4 weeks for up to 49 weeks and a maximum of 13 doses
- Cohort C: a single SC dose of 60 mg once every 4 weeks for up to 49 weeks and a maximum of 13 doses
- Cohort D: a single SC dose of 20 mg every 2 weeks for up to 51 weeks and a maximum of 26 doses
- Cohort E: a single SC dose of 20 mg every week (weekly) for up to 52 weeks and a maximum of 52 doses

Self-administration will be allowed after appropriate training of patient and/or caregiver.

Patients in Cohorts A, B, and C should receive 1 dose every 4 weeks, patients in Cohort D should receive 1 dose every 2 weeks and Cohort E should receive 1 dose per week with weeks always defined relative to Study Day 1. For example if a patient receives the first dose on a Monday, subsequent doses should be

given on Mondays according to the respective dosing schedule, if possible. If a patient misses an injection, or if dosing on the usual day is not possible, the patient can reschedule the injection provided that 2 doses are administered at least 2 days apart.

Every effort should be made to ensure the previous dose is given 7 days prior to a scheduled clinic visit.

Please refer to the Study Drug Manual provided by the Sponsor or designee for more detailed instructions for Study Drug (ISIS 681257 or placebo) preparation and administration.

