**PROTOCOL SYNOPSIS *Continued***

Pharmacokinetic Evaluations
	
Plasma samples will be taken from all patients for the measurement of ISIS 681257 plasma trough levels throughout treatment and during the post-treatment follow-up period. In addition, in a subset of patients (approximately 12 patients per cohort), more frequent plasma samples will be taken following the first and Day 169 (for Cohorts A, B, and C) or Day 183 (for Cohorts D and E) dose to determine PK parameters. Plasma sample collection time points are detailed in Appendices A and C.
 
The plasma ISIS 681257 levels over time will be descriptively summarized by treatment with stratification by subject immunogenicity status. Apparent terminal elimination half-life will be calculated in patients who received ISIS 681257 treatment using a non-compartmental method, if data permitted. In addition, <math>C_{max}</math>, <math>T_{max}</math>, and AUC values will be calculated for the PK subgroup. PK parameters will be descriptively summarized by treatment with stratification by subject immunogenicity status.

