#### **3.4.2 Treatment**

For each patient, minimum treatment duration is 6 months and maximum is 52 weeks.

All patients enrolled will be randomized to a minimum of 6 months of treatment in 1 of 5 treatment cohorts. On completion of the 6 months, patients may continue treatment within the same randomized cohort until the last patient reaches 6 months of exposure (for continuing safety assessments), with a maximal exposure period of 12 months. End of Treatment visits for all patients on treatment will be scheduled no later than the End of Treatment visit of the last patient to complete 6 months of exposure.

The End of Treatment visit should be scheduled one dosing interval post last dose of study drug: one week post last dose for weekly dosing (Cohort E), 2 weeks post last dose for every 2-week dosing (Cohort D), and 4 weeks post last dose for every 4-week dosing (Cohort A-C). The procedures scheduled for the Week 53/ET visit ([Appendix A](#)) will be performed at the End of Treatment visit. Following the End of Treatment visit patients will then enter a 16-week post-treatment follow-up period.

Eligible patients will report to the Study Center for assessments at specified intervals throughout the 52-week treatment period as detailed in the Schedule of Procedures in [Appendix A](#). During the Treatment, Study Drug (ISIS 681257 or placebo) will be administered by SC injection once-weekly, every 2 weeks, or every 4 weeks, depending on cohort assignment.

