**Appendix A Schedule of Procedures – Weekly and Every 2-Week Dosing *Continued***

Study Week	Screen	Treatment Period																	Follow-up Period			
	-4 to -1	1	1	5	9	13	17	21	25	27 p			29	33	37	41	45	49	53/ET	4*	10*	16*
Study Day	-28 to -1	1	2 a	29	57	85	113	141	169	183	184 a	185 a	197	225	253	281	309	337	365	*Post Treatment Period		
Visit and Testing Window +/- Days	0	-3 b	0	2	2	2	3	3	3	3	0	0	3	3	3	3	3	3	3	3	3	3
FSH (women only, if applicable) i, m	X																					
Serum Pregnancy Test m	X	X		X	X	X	X	X	X				X	X	X	X	X	X	X	X	X	X
Archived Serum & Plasma Samples i, n		X			X		X			X					X		X		X	X	X	X
PD Panel j	X	X		X	X	X	X	X		X			X		X		X		X	X	X	X
Lipid Panel j	X	X		X	X	X	X	X		X			X		X		X		X	X	X	X
Lp(a) Characterization		X																				
Study Drug: SC Injection		WEEKLY SUBCUTANEOUS ADMINISTRATION OF STUDY DRUG (Week 1 through Week 52/Day 358) o EVERY 2-WEEK SUBCUTANEOUS ADMINISTRATION OF STUDY DRUG (Week 1 through Week 51/Day 351) o																				
Adverse Events	X	X	X	X	X	X	X	X	X	X	X	X	X	X	X	X	X	X	X	X	X	X
Concomitant Medication	X	X	X	X	X	X	X	X	X	X	X	X	X	X	X	X	X	X	X	X	X	X

All procedures and study samples are to be done pre-dose at respective visits, unless specified

- a Visit only required for patients in PK subgroup.
- b Day 1/Baseline assessments can be performed up to 3 days (-3 days) prior to the actual Day 1 visit, which is the day of first Study Drug dose.
- c Patient charts will be reviewed in order to collect disease associated medical history data such as CVD history.
- d Height only required at Screening.
- e All tests listed in [Appendix B](#) under Extended Urinalysis should be performed, including routine urinalysis, urine microscopy, UACR and UPCR.
- f Assessments and procedures to be conducted by either a home healthcare service or the Study Center. Patient Study Center visits must be no more than 4 weeks apart during the treatment period.
- g Urine samples for renal biomarkers will be collected. Sample analysis will be conducted in accordance with Safety Monitoring for Renal Function ([Section 8.5.2](#)).
- h During follow-up period, hematology sampling for platelet values and urine renal biomarker samples are taken every 14 days for 6 weeks post treatment period, then at Week 10 and Week 16 Follow-up visits.

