**Appendix A Schedule of Procedures – Every 4-Week Dosing *Continued***

	Screen	Treatment Period																			Follow-up Period			
Study Week	-4 to -1	1	1	5	9	13	17	21	25 p		26	27	29	33	37	41	45	49	53/ET	4*	10*	16*		
Study Day	-28 to -1	1	2 a	29	57	85	113	141	169	170 a	171 a	176 a	183 a	197	225	253	281	309	337	365	*Post Treatment Period			
Visit and Testing Window +/- Days	0	-3 b	0	2	2	2	3	3	3	0	0	3	3	3	3	3	3	3	3	3	3	3	3	
FSH (women only, if applicable) j, m	X																							
Serum Pregnancy Test m	X	X		X	X	X	X	X	X					X	X	X	X	X	X	X	X	X	X	
Archived Serum & Plasma Samples j, n		X		X		X		X					X		X		X		X		X	X	X	
PD Panel j	X	X		X	X	X	X	X	X				X	X		X		X		X		X	X	
Lipid Panel j	X	X		X	X	X	X	X	X			X	X	X		X		X		X		X	X	
Lp(a) Characterization		X																						
Study Drug: SC Injection		EVERY 4-WEEK SUBCUTANEOUS ADMINISTRATION OF STUDY DRUG (Week 1 through Week 49/Day 337) o																						
Adverse Events	X	X	X	X	X	X	X	X	X	X	X	X	X	X	X	X	X	X	X	X	X	X	X	
Concomitant Medication	X	X	X	X	X	X	X	X	X	X	X	X	X	X	X	X	X	X	X	X	X	X	X	

All procedures and study samples are to be done pre-dose at respective visits, unless specified

- a Visit only required for patients in PK subgroup.
- b Day 1/Baseline assessments can be performed up to 3 days (-3 days) prior to the actual Day 1 visit, which is the day of first Study Drug dose.
- c Patient charts will be reviewed in order to collect disease associated medical history data such as CVD history.
- d Height only required at Screening.
- e All tests listed in [Appendix B](#) under Extended Urinalysis should be performed, including routine urinalysis, urine microscopy, UACR and UPCR.
- f Assessments and procedures to be conducted by either a home healthcare service or the Study Center. Patient Study Center visits must be no more than 4 weeks apart during the treatment period.
- g Urine samples for renal biomarkers will be collected. Sample analysis will be conducted in accordance with Safety Monitoring for Renal Function ([Section 8.5.2](#)).
- h During follow-up period, hematology sampling for platelet values and urine renal biomarker samples are taken every 14 days for 6 weeks post treatment period, then at Week 10 and Week 16 Follow-up visits.

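### Section 8.1 sets a 7-day gap between the previous dose and a clinic visit for every cohort; at visits attended by all patients this fits only weekly Cohort E (minor wording error)

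*Protocol*

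**What the plan says.** Section 8.1 of the Protocol (Amendment 6) doses Cohorts A-C every 4 weeks, Cohort D every 2 weeks and Cohort E weekly, "with weeks always defined relative to Study Day 1". A missed or displaced injection may be rescheduled if two doses are at least 2 days apart. Then, as a separate paragraph with no cohort named, comes the instruction: "Every effort should be made to ensure the previous dose is given 7 days prior to a scheduled clinic visit". The same section states: "Self-administration will be allowed after appropriate training of patient and/or caregiver".

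Other parts of the Protocol fix the timing by cohort:

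- Appendix A, 4-week schedule: "EVERY 4-WEEK SUBCUTANEOUS ADMINISTRATION OF STUDY DRUG (Week 1 through Week 49/Day 337".
- Appendix A, weekly and 2-week schedule: "EVERY 2-WEEK SUBCUTANEOUS ADMINISTRATION OF STUDY DRUG (Week 1 through Week 51/Day 351" for Cohort D, with weekly doses running to Week 52 (Day 358) for Cohort E.
- Both Appendix A schedules: "All procedures and study samples are to be done pre-dose at respective visits, unless specified".
- Section 3.4.2 puts the End of Treatment visit one dosing interval after the last dose. That is one week for Cohort E and, for the others, "2 weeks post last dose for every 2-week dosing (Cohort D), and 4 weeks post last dose for every 4-week dosing (Cohort A-C".

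No text restricts the 7-day sentence to Cohort E.

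**The concern.** A general instruction in the dosing section disagrees with the specific schedule, with the End of Treatment rule and with the dosing frequencies set out just before it. The sentence cannot be followed in Cohorts A-D at visits attended by all patients without leaving the Day 1-anchored schedule.

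The visits concerned carry the primary Lp(a) sample (Week 25 in A-C, Week 27 in D and E). They also carry the trough PK samples; the Synopsis says: "Plasma samples will be taken from all patients for the measurement of ISIS 681257 plasma trough levels throughout treatment". A site or patient who moved a dose to 7 days before such a visit would take both samples off trough. The disturbance would be larger in the 4-week cohorts than in Cohort D. It would therefore also affect unequally the comparison of 20 mg every 2 weeks with 40 mg every 4 weeks described in Section 2.4.

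**Working it through.** **1. Dose days.** Dose day k = 1 + (k − 1) × interval, up to the last dose day in Appendix A.

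- A-C: interval 28, Days 1, 29, …, 337. Count: (337 − 1)/28 + 1 = 13.
- D: interval 14, Days 1, 15, …, 351. Count: (351 − 1)/14 + 1 = 26.
- E: interval 7, Days 1, 8, …, 358. Count: (358 − 1)/7 + 1 = 52.

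These counts match Table 2, so the dose calendar is reproduced.

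**2. Gap at visits attended by all patients.** Gap = visit day − latest earlier dose day. Visits after Day 1 are Days 29, 57, 85, 113, 141, 169, 197, 225, 253, 281, 309, 337 and 365, plus Day 183 for D and E.

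| Cohort | Visits | Gap at each | Primary visit | Day 365 visit |
|---|---|---|---|---|
| A-C | 13 | 28 days | 169 − 141 = 28 | 365 − 337 = 28 |
| D | 14 | 14 days | 183 − 169 = 14 | 365 − 351 = 14 |
| E | 14 | 7 days | 183 − 176 = 7 | 365 − 358 = 7 |

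The stated 7 days is reproduced for Cohort E and for no other cohort.

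**3. Visits for the PK subgroup only.** In A-C, Days 170, 171, 176 and 183 fall 1, 2, 7 and 14 days after the Day 169 dose. In D and E, Days 184 and 185 fall 1 and 2 days after the Day 183 dose. Outside Cohort E, a 7-day gap occurs once, at Day 176 in A-C.

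**4. What following the sentence would require at the primary visit.**

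- A-C: 169 − 7 = Day 162 instead of Day 141, a shift of 21 days. The gaps become 162 − 113 = 49 days, then 7 days.
- D: 183 − 7 = Day 176 instead of Day 169, a shift of 7 days. The gaps become 176 − 155 = 21 days, then 7 days.

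The visit window at these visits is ±3 days.

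**5. Illustrative drug level if only that one dose moved.** Assumption: simple exponential decline with the 3 to 4 week terminal half-life of Section 2.3.4 (21 to 28 days), equal doses, and residual drug from earlier doses included. Level, in units of one dose = Σ 2^(−(visit day − dose day)/half-life).

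| Cohort | Half-life | As scheduled | Dose moved | Ratio |
|---|---|---|---|---|
| A-C (6 doses, Day 169) | 21 d | 0.655 | 1.052 | 1.61 |
| A-C | 28 d | 0.984 | 1.325 | 1.35 |
| D (13 doses, Day 183) | 21 d | 1.698 | 1.862 | 1.10 |
| D | 28 d | 2.388 | 2.521 | 1.06 |

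For example, in A-C at 28 days, removing the Day 141 term (2^(−28/28) = 0.5) and adding a Day 162 term (2^(−7/28) = 0.841) gives 0.984 − 0.5 + 0.841 = 1.325.

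**The case against.** The strongest reply is that the dose in question is pinned down elsewhere. Day 141 in A-C and Day 169 in D are themselves scheduled clinic visits, and Appendix C requires a pre-dose PK sample from all patients on those days. To follow the 7-day sentence, a site would have to draw that sample, withhold the dose, and give it 21 or 7 days later on a day with no scheduled dose. In A-C all 13 dose days are clinic visits, so self-administration adds little risk there. The wording is also soft. This stands, and it makes the harm remote.

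A second reply is that the sentence follows the text on rescheduled injections and may only be meant to keep a made-up dose away from a visit. That may be the intent, but the sentence does not say so. It gives 7 days, not a minimum, whereas the preceding paragraph does state a minimum for the spacing of two doses. A Study Drug Manual is also mentioned for preparation and administration detail; it is not available here, so whether it clarifies the point is unknown.

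Two stronger readings are tempting and not supported. A reader might infer that the primary Lp(a) comparison is compromised. The schedule itself is correct and consistent, nothing shows that sites would depart from it, and the ratios above concern drug level under a simplified model (Section 2.3.4 describes biphasic decline). The document gives no basis for converting them to Lp(a). A reader might also infer that 7 days matches no visit outside Cohort E. It does match Day 176 for the PK subgroup in A-C, so the mismatch must be stated for visits attended by all patients.

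**Conclusion.** The inconsistency is real and minor. Section 8.1 contains an operative instruction that is wrong as written for Cohorts A-D at every on-treatment visit after Day 1 attended by all patients. The correct gap is one dosing interval, as Appendix A and Section 3.4.2 already have it. This part rests only on the stated dose and visit days.

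The consequence is conditional on someone acting on the sentence. If only the dose before the primary visit moved, the drug level at sampling would be about 1.35 to 1.61 times scheduled trough in A-C and 1.06 to 1.10 times in D, under the exponential assumption. The specific schedule would most likely prevail, so an effect on the primary Lp(a) sample is possible but unlikely. No effect on power, error rate or the planned analysis is shown.

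**What to change.** Keep the opening of the sentence and change its ending, so that the previous dose is to be given *one dosing interval (28 days for Cohorts A-C, 14 days for Cohort D, 7 days for Cohort E) before each scheduled on-treatment clinic visit attended by all patients, including the End of Treatment visit*.

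The limit to visits attended by all patients is needed. Without it, the new wording would be wrong for the PK-subgroup-only visits (Days 170, 171, 176 and 183 in A-C; Days 184 and 185 in D and E) and for the follow-up visits. Early-termination visits keep their own timing under Section 8.8.1.

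The cost is one sentence, by clarification letter or with the next amendment. No new data or analysis is required.
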